### **Other Variables of Interest and Their Measurements**

Because this is a randomized trial, confounders should be equally distributed between the two treatment groups. All variables will be analyzed to check if there are any differences between the two groups.

There will be many variables collected for this study. These variables include the pain score evaluations, ages, genders, patient related contact information, comorbidities, tobacco use, medications, allergies, BMIs, laboratory results, all anesthesia medications used, number of millimeters the capital fragment was transposed, fixation specifics for the bunionectomies, intra-operative complications, tourniquet time, attending of record, attending experience, pain control given in post-anesthesia holding area, pain medication taken post-operatively, pill counting and mechanisms to assess patient compliance post-operatively, timing of the telephone interview and last dose of post-operative pain medication, post-operative protocol deviations, and whether or not physical therapy was used. The study and analysis will take place and be stored at Beth Israel Deaconess Medical Center. Follow-up visits may also occur at Beth Israel Deaconess Medical Center satellite clinics for patient convenience.

## **C. Subject Selection**

### **Assembly of subjects**

All patients undergoing a first metatarsal Kalish osteotomy for bunion correction who meet study inclusion and exclusion criteria will be invited to participate in this study.

### **Inclusion Criteria:**

- Hallux abductus with bunion deformity
- Adult patients as defined by  $\geq 18$  years old and  $\leq 80$  years old
- Subject has adequate perfusion, verified by the surgeon, which is defined by palpable pedal pulses
- Subject has voluntarily signed and dated an informed consent form, approved by an Institutional Review Board, and provided HIPAA (or other applicable privacy regulation) authorization prior to any participation in the study
- Subject agrees not to take any new medications, dietary supplements, or alternative therapies during the study period (approximately 12 weeks)
- Subject is interested in participating in the study and willing to comply with the study protocol
- Patient has pain related to a bunion deformity but pain-free metatarsalphalangeal joint (MTPJ) range of motion that is not functionally adapted
- Adequate bone density to withstand a Kalish bunionectomy procedure
- No frontal plane hallux deformity
- Minimal abnormality of the PASA

- Normal to minimally malaligned sagittal plane position of the first metatarsal
- Failure of conservative treatment
- General Pre-operative Radiographic Angle Criteria†
  - 10-15 IMA in rectus feet\*
  - 20-25 TAA in adducted feet\*
  - 15-20^0 IMA in rectus feet if wide metatarsal head width
  - 25-30^0 TAA in adducted feet if wide metatarsal head width

*IMA=intermetatarsal angle; TAA=total adductus angle*  
\*If the pre-operative IMA is <15, only the IMA will be used pre-operatively. For IMA ≥15, the total adductus angle will be used  
†These are general guidelines and the width of the metatarsal as well as the presence of positional, structural, or combined first ray deformity may also influence procedure selection (51-52).

Exclusion Criteria:

- Patients with a contraindication for ketorolac will be excluded from the study. This includes patients with:
  - a history of an allergic-type reaction in response to exposure to aspirin, phenylacetic acid derivatives, or other NSAIDs
  - hypersensitivity to ketorolac tromethamine, or to any product component
  - any known bleeding risk or bleeding disorder, suspected or confirmed
  - history of or active cerebrovascular bleeding, suspected or confirmed
  - concomitant aspirin or NSAID use where the patient may not be advised to discontinue the medication during the study
  - concomitant pentoxifylline use
  - concomitant probenecid use
  - coronary artery bypass graft (CABG) surgery within one year of the procedure
  - any history of gastrointestinal bleeding/perforation, gastrointestinal ulcer, severe peptic ulcer disease, or severe inflammatory bowel disease
  - hemorrhagic diathesis, suspected or confirmed
  - incomplete intraoperative hemostasis
  - pre-operative serum creatinine > 1.5 ml/dL or blood urea nitrogen level > 22 mg/dL
  - any history of renal impairment or risk of renal failure due to volume depletion
- Patients with a known allergy, contraindication and/or intolerance for oxycodone 5mg – acetaminophen 325 mg will be excluded from the study.
- Patients with a known allergy, contraindication, and/or intolerance for the local anesthetic (bupivacaine) or any of the standardized intra-operative opioids and anti-emetics administered by the anesthesiologist
- Patients with a history of fibromyalgia or opioid abuse
- History of chronic regional pain syndrome or diagnosis of any chronic pain syndrome, patients requiring routine methadone or other opioids
- Neuropathy or radiculopathy
- Subject has alcohol or substance abuse, dementia, brain metastases, or other cognitive disorders that may interfere with pain assessment and the post-operative course outlined by the surgeon

- Patients with a contraindication for elective surgery will be excluded and includes:
  - American Society of Anesthesiologists (ASA) Physical Status class four or higher
  - women who are pregnant, planning on becoming pregnant, or breast feeding
  - presence of active local or systemic infection
  - subject has a myocardial infarction in the last twelve months
  
- Patients who are not candidates for a Kalish bunionectomy due to the preoperative deformity as well as other study exclusions are:
  - Absent pedal pulses or  $ABI \leq 0.9$  and  $\geq 1.2$
  - Concomitant midfoot and rearfoot procedures
  - Moderate to high abnormal PASA angles
  - Significant sagittal plane first metatarsal deformity
  - Moderate to severe osteoporosis as evaluated by preoperative radiographs and/or bone mineral density tests
  - Revision cases
  - History of previous infections, radiation treatment, or current infection related to the surgical site
  - History of previous trauma of the first metatarsal or first ray
  - Subject has known immunosuppression (HIV, recent chemotherapy, organ transplant)
  - Patients taking systemic steroid (patients taking less than 5 mg of prednisone, inhaled steroids for asthma or chronic obstructive pulmonary disease, topical or optical steroids will not be excluded)
  - Subject has active malignancy, excluding cutaneous malignancies except melanoma

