#### **A.4. Screening, Enrollment, and Post-operative Course**

##### *a. Screening, Informed Consent, and Randomization*

All subjects will be treated pre-operatively by his/her surgeon. Once the surgeon determines the patient will require a Kalish bunionectomy, he/she will review the patient's medical record to determine if the patient meets the study inclusion/exclusion criteria. If the investigator/surgeon determines that the patient meets study criteria, he/she will discuss the clinical trial with the patient. If the patient expresses interest in participating in the clinical trial, the investigator/surgeon and/or research fellow will complete a standard screening form to determine the patient's eligibility. All eligible patients will be given a copy of the informed consent form for review. A screening log will be maintained. If the patient has additional questions, he/she will be given the principal investigator's and research fellow's contact information.

On the day of the surgery (*Day 0*), the informed consent will be reviewed again with the patient by one of the investigators. If the patient decides he/she would like to enroll in this study, they will sign the informed consent form, and will be randomized in the pre-operative holding area to either ketorolac or placebo. The patient and surgeon will be blinded to which study drug he/she was randomized to. Baseline information will be recorded including baseline pain scores. Pain will be measured by both unidimensional and multidimensional instruments. This will include the McGill Pain Questionnaire-Short Form (MPQ-SF) and the visual analog scale (VAS). The VAS will be 10 cm in length with the end anchors, "no pain" and "worse possible pain".

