**frequency of clinic visits are all standard of care and do not change as a result of this study.**

The surgeon may deviate if he/she feels it is necessary for a particular patient or if concomitant procedures necessitate a deviation. Any deviations will be recorded and accounted for in the analysis. We do not anticipate any significant protocol deviations. Immediate anteroposterior and lateral radiographs will be taken post-operatively. The patient will be placed in a sterile soft post-operative dressing. Research pharmacy will dispense the study medication (oral ketorolac or placebo) and standardized prescriptions will be given for opioid pain medication. Standard post-operative instructions will be given to all patients. This includes instructions for icing and elevating the foot, as well as medication instructions. Patients will be allowed to partial weight bear in a post-operative shoe with crutches due to the inherent stability of the osteotomy, given that rigid internal fixation is provided as detailed in the surgical technique. Patients will be given a study diary with instructions on how to properly record information. The post-operative care described here is considered standard of care for this procedure (except for the study drug and study diary) and not related to the study.

*c. Day Two:* Patients will be contacted by telephone two days (48 hours,  $\pm 4$  hours after the surgical procedure) by a dedicated research fellow trained in survey administration between the hours of 8am and 6pm. This person has no involvement with the surgical procedure and is blinded to the patient's randomization status. This will allow enough time for the affects of anesthesia to subside, 48 hours ( $\pm 4$  hours) following his/her surgery. This will also be well within the five day window in which the patient will be taking ketorolac post-operatively.

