#### **A.7. Study Endpoints**

The study will be concluded once each patient achieves radiographic union at 12 weeks (please refer to grading scale in the statistical consideration section) or up to six months, whichever comes first. If a patient experiences a serious adverse event, requiring them to discontinue the study medication, they will be immediately withdrawn from the study, treated appropriately, and reported.

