**Thus, the previously noted 88 total sample size (44 patients per treatment arm) was estimated to**

**be adequate to achieve study aims and goals.**

**b. Data Analysis**

**Outcomes and their Measurements**

*a. Primary Outcome*

All analyses will be calculated using Statistical Analysis Software (SAS, Worldwide Headquarters, Cary, NC) and will be based on the **intention-to-treat principle**.

The primary outcome of interest is pain measured on the second post-operative day, 48 hours ( $\pm 4$  hours) following surgery. This will allow the effects of anesthesia to subside following surgery. This will be well within the five day window in which the patient will be taking ketorolac post-operatively.

Pain will be measured by both unidimensional and multidimensional instruments. A blinded trained research fellow will contact patients by telephone and will administer the McGill Pain Questionnaire-Short Form (MPQ-SF) and instruct patients to fill out the visual analog scale (VAS). This will occur 48 hours ( $\pm 4$  hours) post-operatively. The VAS will be pre-printed in a diary that is given to the patient post-operatively. The VAS will be 10 cm in length with the end anchors, "no pain" and "worst pain possible". If patient compliance with the VAS is greater than 95%, then the VAS will be used for the primary analysis. As a back-up, the MPQ-SF will be utilized as the primary analysis. Regardless, sensitivity analyses will be conducted to verify the robustness of the results. The research fellow will also obtain the patient's post-operative pain medication consumption (including timing and dosages) and verbally confirm study protocol compliance during this telephone interview (Please refer to the variables collected section for full details; A telephone script is also included in this IRB application). Regression will be utilized to control for measured confounders, including timing of the telephone interview and last dose of post-operative pain medication. Standard regression model rules will be applied and a p-value  $\leq 0.05$  will be considered statistically significant in the final regression model.

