#### **Missing Data**

Given that the first outcome measure occurs within two days and the second outcome occurs in twelve weeks of study enrollment, we do not anticipate that missing data will be a large concern. Protocol deviations will be recorded and reported but the primary analysis will be an **intent-to-treat analysis**. For outcomes requiring a longer follow-up duration, any patients who are lost, move or expire will be counted as treatment failures. Patients will be generally healthy as this is a population undergoing elective bunionectomy surgery. In addition, information will be collected regarding patient contact information to help prevent loss of patients. Patients that miss a follow-up appointment will have a set mechanism in-place in order to contact the patients. All available contact information

including the patient's residential and work address, work, home and cellular phone number as well as contact information of the next of kin and closest friend will be obtained for each patient. Permission to contact these people as necessary will be obtained. The short follow-up period will also improve success in these measures. Finally, there is a built in 10% increase in patient sample size if the above safety measures still fail.

Although we do not anticipate significant missing data problems, any concerns will be dealt with sensitivity analyses to determine their impact.

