#### **Enrollment**

On the day of the surgery (Day 0), the informed consent will be reviewed again with the patient by one of the study investigators. The Investigator will be responsible for obtaining written informed consent from each patient. If the patient decides to enroll into the study, the patient will sign the informed consent in the pre-operative holding area prior to his/her surgery and prior to receiving any anesthesia-related medications. Once the patient has signed the informed consent form, he/she will be randomized in the pre-operative holding area and enrolled into the study.

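### Incomplete intraoperative hemostasis is listed as an exclusion but can only be seen after randomisation, so applied as written it conflicts with intention-to-treat

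*Combined protocol and SAP*

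**What the plan says.** Under Exclusion Criteria (B3, section C, Subject Selection), the ketorolac contraindications open with "Patients with a contraindication for ketorolac will be excluded from the study". One item beneath that sentence is "incomplete intraoperative hemostasis".

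Section A.4.a says that a consenting patient "will be randomized in the pre-operative holding area to either ketorolac or placebo" on the day of surgery. Section A.6 gives the same place, and the Enrollment paragraph of B6 says "he/she will be randomized in the pre-operative holding area and enrolled into the study".

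On analysis, the Primary Outcome text states "All analyses will be calculated using Statistical Analysis Software (SAS, Worldwide Headquarters, Cary, NC) and will be based on the" intention-to-treat principle. The Missing Data section adds "Protocol deviations will be recorded and reported but the primary analysis will be an" intent-to-treat analysis. Section A.4.b says of departures from the post-operative course: "Any deviations will be recorded and accounted for in the analysis". Section A.3 has a similar sentence for intra-operative departures.

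Section A.7 covers a serious adverse event "requiring them to discontinue the study medication, they will be immediately withdrawn from the study, treated appropriately, and reported". B5 lets the surgeon decide whether a patient should discontinue the study. Neither place says whether outcomes are still collected.

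**The concern.** The neighbouring contraindications, such as allergy, bleeding history, renal function and interacting drugs, can be checked before randomisation. Hemostasis during surgery cannot. An exclusion that takes effect after allocation removes randomised patients because of something that happened later, which intention-to-treat analysis is meant to prevent.

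Calling the analysis intention-to-treat does not settle the matter, because it needs outcome data. Section A.3 identifies the telephone call, diary and questionnaires as study-specific, and all of the post-operative ones come after the point at which the patient would be excluded. Such a patient would probably have no 48-hour VAS (the primary outcome) and no diary adverse-event form. Surgeons could also handle the same situation differently, since the exclusion list points one way and the deviation rule the other.

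A.7 repeats the pattern by treating the end of study drug as the end of study participation. It is a parallel issue. Nothing says that incomplete hemostasis is a serious adverse event, so A.7 does not govern it.

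**Working it through.** **Order of events**

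1. Consent, randomisation and enrolment: pre-operative holding (A.4.a, A.6, B6 Enrollment).
2. Surgery, with the IV study dose given in the operating room (A.5). Its order relative to any judgement of hemostasis is not fixed.
3. Closure and dressing, then tourniquet release (A.3).
4. Diary and capsules dispensed (A.4.b), 48-hour call (A.4.c), diary collected at week one (A.4.d).

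The criterion can be met only at step 2 or 3, always after step 1.

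**The plan's own figure.** 80 × 1.10 = 88, or 44 per arm, as stated in the Sample Size Justification. The 10% is for drop-outs and contact difficulties; post-randomisation exclusions are not mentioned.

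**Implied SD.** No SD is given, so it is back-solved (normal approximation) from 40 per arm, difference 1.3, 80% power and two-sided 0.05:

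SD = 1.3 / (1.960 + 0.842) × √(40/2) = 2.08.

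This is an effective SD. Dividing by √1.72, where 1.72 = 1 + 9 × 0.08 is the design effect, gives 1.58; the power results are the same either way. The plan's second pair (1.8, 20 per arm) implies 2.03, which is consistent.

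**Power with 44 per arm and no loss.** Standard error = 2.075 × √(2/44) = 0.442. Power = Φ(1.3/0.442 − 1.960) = 83.6%.

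**Number affected.** The documents give no frequency. I assume 1 to 5%; nothing in them supports the upper end. The expected number is 0.01 × 88 = 0.9 to 0.05 × 88 = 4.4.

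**Removed or kept.** *Removed* takes a fraction p from both arms, so n = 44(1 − p). *Kept* assumes that a fraction p of the ketorolac arm gets no benefit at all, so the difference is 1.3(1 − p).

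| p | Removed: n per arm | Power | Kept: difference | Power |
|---|---|---|---|---|
| 1% | 43.56 | 83.2% | 1.287 | 82.9% |
| 2% | 43.12 | 82.9% | 1.274 | 82.1% |
| 5% | 41.80 | 81.7% | 1.235 | 79.7% |

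**Extreme-case bias.** If k of 44 patients are removed from one arm only, and their 48-hour VAS would have differed by x from the rest, the arm mean shifts by k·x/44. With x = 2 (an assumption):

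- k = 1: 2/44 = 0.045, or 3.5% of 1.3.
- k = 4: 8/44 = 0.18, or 14% of 1.3.

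**The case against.** The strongest reply is that the plan already keeps these patients. All analyses are intention-to-treat, deviations are recorded without changing the primary analysis, and the compliers-only analysis in Secondary Outcomes is set apart from the randomised comparison, which implies that patients who do not take study drug stay in it. Missing Data also promises sensitivity analyses. This is a fair reading of who should be analysed. It does not displace the explicit exclusion sentence, and it cannot supply a 48-hour VAS that nobody collected. No section expressly says that collection stops, so the data loss is a probable consequence, not a stated one.

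A reader might infer that removal would differ by arm, because ketorolac could itself cause the bleeding. The documents do not show this. It requires bleeding to be judged after the IV dose. A.5 leaves the order open, and the only text on timing within surgery (B2, Preliminary Studies) describes prior practice: a dose near the end of the case when there are no contraindications. That is background and not a trial rule, but it favours judgement before dose. In that order, removal by blinded staff costs precision only. The late tourniquet release keeps the other order possible, though bleeding first seen after closure may not count as intraoperative.

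A reader might also infer that sites would differ, or that healing and safety data would be lost wholesale. B6 describes recruitment from one institution with satellite offices, so any inconsistency is between surgeons. Radiographs and clinic visits are standard care, and B5 has all adverse events reported and gives patients an on-call number.

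Finally, keeping these patients costs more power than removing them. That is true, and it is the price of the fix.

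**Conclusion.** The contradiction is real: one criterion in the exclusion list can take effect only after randomisation, and the analysis plan does not allow for that. A.7 has the same fault for serious adverse events. The practical consequence is probably a missing 48-hour VAS and diary adverse-event form for a few patients.

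The size is probably small. Known or suspected bleeding risk is already excluded. Even four removals, all in one arm and all 2 points different, move that arm's mean by 0.18 against 1.3; both conditions are assumptions. The case for changing the text is protection from post-randomisation exclusion, fuller safety data and one clear instruction for surgeons. It is not a gain in power. Minor priority.

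**What to change.** Take the item out of the exclusion list and make it a treatment rule. Suggested text:

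*If the surgeon judges intraoperative hemostasis incomplete before the IV dose, blinded study drug is withheld. If the IV dose has been given, the capsules are not started or are stopped. The patient stays in the assigned arm for the intention-to-treat analysis and has the diary, 48-hour call, adverse events and week-12 radiograph collected. The number of such patients is reported by arm, with whether the IV dose had been given.*

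The rule covers stopping as well as withholding because the tourniquet is released only after the dressing.

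Amend A.7 in the same way:

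*If a serious adverse event requires stopping study medication, the medication is stopped, the patient is treated and the event is reported. Follow-up continues in the assigned arm unless the patient withdraws consent.*

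The cost is wording in two places, plus a diary and one call for a few patients; the week-12 radiograph is already standard care. The statistical downside is dilution: at the assumed 5% with no drug benefit, power is 79.7% if these patients are kept against 81.7% if they are removed, a difference of 2 points. At 1% the difference is 0.3 points.

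Randomising only after hemostasis is confirmed would also remove the conflict. It would move allocation and preparation of the IV dose into the operation, could miss bleeding seen after tourniquet release, and would leave A.7 unchanged.
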